### Informed Consent

5. Capable of giving signed informed consent as described in Section 10.1 (Appendix 1), which includes compliance with the requirements and restrictions listed in the ICF and in this protocol

## 5.2. Exclusion Criteria

Participants are excluded from study enrollment if they meet any of the following criteria:

### Medical Conditions

#### *Diabetes-Related*

6. Have Type 1 diabetes mellitus (T1DM) or T2DM, history of ketoacidosis, or hyperosmolar state/coma
7. Have at least 1 laboratory value suggestive of diabetes mellitus during screening, including 1 or more of: HbA1c  $\geq 6.5\%$  ( $\geq 48$  mmol/mol), fasting glucose  $\geq 126$  mg/dL ( $\geq 7.0$  mmol/L), and random glucose  $\geq 200$  mg/dL ( $\geq 11.1$  mmol/L)

#### *Obesity-Related*

8. Have a self-reported change in body weight  $>5$  kg within 3 months prior to screening
9. Have a prior or planned surgical treatment for obesity (excluding liposuction or abdominoplasty if performed  $>1$  year prior to screening)
10. Have or plan to have endoscopic and/or device-based therapy for obesity or have had device removal within the last 6 months prior to screening

#### **Examples:**

- mucosal ablation
- gastric artery embolization
- intragastric balloon
- duodenal-jejunal endoluminal liner

#### *Other Medical*

11. Have renal impairment measured as estimated glomerular filtration rate (eGFR)  $<30$  mL/min/1.73 m^2, calculated by Chronic Kidney Disease-Epidemiology as determined by central laboratory during screening
12. Have a known clinically significant gastric emptying abnormality (for example, severe gastroparesis or gastric outlet obstruction) or chronically take drugs that directly affect GI motility
13. Have a history of chronic or acute pancreatitis
14. Have thyroid-stimulating hormone (TSH) outside of the range of 0.4 to 6.0 mIU/L at the screening visit

**Note:** Participants receiving treatment for hypothyroidism may be included, provided their thyroid hormone replacement dose has been stable for at least 3 months and their TSH at screening falls within the range indicated above.

**Note:** Participants with a history of subclinical hypothyroidism but a TSH at screening within the range indicated above, may be included if, in the investigator's opinion, the

patient is unlikely to require initiation of thyroid hormone replacement during the course of the study.

15. Have obesity induced by other endocrinologic disorders (for example, Cushing syndrome) or diagnosed monogenetic or syndromic forms of obesity (for example, Melanocortin 4 Receptor deficiency or Prader Willi Syndrome)
16. Have a history of significant active or unstable major depressive disorder (MDD) or other severe psychiatric disorder (for example, schizophrenia, bipolar disorder, or other serious mood or anxiety disorder) within the last 2 years

**Note:** Participants with MDD or generalized anxiety disorder whose disease state is considered stable for the past 2 years and expected to remain stable throughout the course of the study, in the opinion of the investigator, may be considered for inclusion if they are not on excluded medications.

17. Have a lifetime history of suicide attempt
18. Have a PHQ-9 score of 15 or more on or before Visit 2
19. On the C-SSRS on or before Visit 2:
  - a “yes” answer to Question 4 (Active Suicidal Ideation with Some Intent to Act, Without Specific Plan) on the “Suicidal Ideation” portion of the C-SSRS  
**or**
  - a “yes” answer to Question 5 (Active Suicidal Ideation with Specific Plan and Intent) on the “Suicidal Ideation” portion of the C-SSRS  
**or**
  - a “yes” answer to any of the suicide-related behaviors (actual attempt, interrupted attempt, aborted attempt, preparatory act or behavior) on the “Suicidal Behavior” portion of the C-SSRS  
**and**
  - the ideation or behavior occurred within the past month
20. Have uncontrolled hypertension (systolic blood pressure above or equal to 160 mmHg and/or diastolic blood pressure above or equal to 100 mmHg)
21. Have any of the following cardiovascular conditions within 3 months prior to Visit 2
  - acute myocardial infarction
  - cerebrovascular accident (stroke)
  - unstable angina
  - hospitalization due to congestive heart failure (CHF)
22. Have NYHA Functional Classification Class IV CHF
23. Have acute or chronic hepatitis, signs and symptoms of any other liver disease other than nonalcoholic fatty liver disease (NAFLD), or any of the following, as determined by the central laboratory during screening:

- alanine aminotransferase (ALT) level  $>3.0X$  upper limit of normal (ULN) for the reference range
- alkaline phosphatase (ALP) level  $>1.5X$  ULN for the reference range, or
- total bilirubin (TBL) level  $>1.2X$  ULN for the reference range (except for cases of known Gilbert's Syndrome)

**Note:** Participants with NAFLD are eligible to participate in this trial if their ALT level is  $\leq 3.0X$  ULN for the reference range

24. Have a serum calcitonin level (at Visit 1) of:

- $\geq 20$  ng/L, if eGFR  $\geq 60$  mL/min/1.73 m^2
- $\geq 35$  ng/L, if eGFR  $<60$  mL/min/1.73 m^2

25. Have a family or personal history of medullary thyroid carcinoma (MTC) or multiple endocrine neoplasia (MEN) syndrome type 2

26. Have a history of an active or untreated malignancy or are in remission from a clinically significant malignancy (other than basal or squamous cell skin cancer, in situ carcinomas of the cervix, or in situ prostate cancer) for less than 5 years

27. Have any other condition not listed in this section (for example, hypersensitivity or intolerance) that is a contraindication to GLP-1R agonists

28. Have a history of any other condition (such as known drug or alcohol abuse, diagnosed eating disorder, or other psychiatric disorder) that, in the opinion of the investigator, may preclude the participant from following and completing the protocol

29. Have history of use of marijuana or tetrahydrocannabinol (THC)-containing products within 3 months of enrollment or unwillingness to abstain from marijuana or THC-containing products use during the trial.

**Note:** If a participant has used cannabidiol oil during the past 3 months but agrees to refrain from use for the duration of the study, the participant can be enrolled.

30. Have had a transplanted organ (corneal transplants [keratoplasty] allowed) or awaiting an organ transplant

31. Have any hematological condition that may interfere with HbA1c measurement (for example, hemolytic anemias, sickle cell disease)

### Prior/Concomitant Therapy

32. Are receiving or have received within 3 months prior to screening chronic ( $>2$  weeks or  $>14$  days) systemic glucocorticoid therapy (excluding topical, intraocular, intranasal, intra-articular, or inhaled preparations) or have evidence of a significant, active autoimmune abnormality (for example, lupus or rheumatoid arthritis) that has required (within the last 3 months) or is likely to require, in the opinion of the investigator, concurrent treatment with systemic glucocorticoids (excluding topical, intraocular, intranasal, intra-articular, or inhaled preparations) during the course of the study

33. Have current or history of (within 3 months prior to Visit 2) treatment with medications that may cause significant weight gain, including but not limited to: tricyclic antidepressants, atypical antipsychotics, and mood stabilizers

**Examples:**

- imipramine
- amitriptyline
- mirtazapine
- paroxetine
- phenelzine
- chlorpromazine
- thioridazine
- clozapine
- olanzapine
- valproic acid (and its derivatives), or
- lithium

*Note:* Selective serotonin reuptake inhibitors other than paroxetine are permitted.

34. Have taken, within 3 months prior to Visit 2, medications (prescribed or over-the-counter) or alternative remedies that promote weight loss

**Examples include, but are not limited to:**

- Saxenda (liraglutide 3.0 mg)
- Xenical®/Alli® (orlistat)
- Meridia® (sibutramine)
- Acutrim® (phenylpropanolamine)
- Sanorex® (mazindol)
- Apidex® (phentermine)
- BELVIQ® (lorcaserin)
- Bontril® (phendimetrazine)
- Qsymia™ (phentermine/topiramate combination), or
- Contrave® (naltrexone/bupropion)

*Note:* Use of metformin or any other glucose-lowering medication, whether prescribed for polycystic ovary syndrome (PCOS) or diabetes prevention, is not permitted.

35. Have started implantable or injectable contraceptives (such as Depo Provera®) within 18 months prior to screening

**Prior/Concurrent Clinical Study Experience**

36. Are currently enrolled in any other clinical study involving an investigational product (IP) or any other type of medical research judged not to be scientifically or medically compatible with this study

37. Within the last 30 days, have participated in a clinical study and received treatment, whether active or placebo. If the study involved an IP, 5 half-lives or 30 days, whichever is longer, should have passed
38. Have previously completed or withdrawn from this study or any other study investigating tirzepatide after receiving at least 1 dose of IP

## Other Exclusions

39. Are investigator site personnel directly affiliated with this study and/or their immediate families. Immediate family is defined as a spouse, parent, child, or sibling, whether biological or legally adopted
40. Are Lilly employees

## 5.3. Lifestyle Considerations

Per the SoA (Section 1.3), participants will consult with a dietitian, or equivalent qualified delegate, according to local standards, to receive lifestyle management counseling at Weeks 0, 4, 8, and 12 during dose escalation and then at Weeks 24, 36, 40, 52, 64, 76, and 88.

Diet and exercise goals established during the lifestyle consultation and the importance of adherence to the lifestyle component of the trial will be reinforced at each trial contact by study staff.

### 5.3.1. Meals and Dietary Restrictions

At Visit 2 and subsequent visits, study participants will receive dietary counseling by a dietitian, or equivalent qualified delegate, according to local standard. Dietary counseling will consist of advice on healthy food choices and focus on calorie restriction using a hypocaloric diet with macronutrient composition of:

- maximum 30% of energy from fat,
- approximately 20% of energy from protein,
- approximately 50% of energy from carbohydrates, and
- an energy deficit of approximately 500 kcal/day compared to the participant's estimated total energy expenditure (TEE).

To encourage adherence, it is recommended that a 3-day diet and exercise log be completed prior to each counseling visit. During each visit, the participant's diet will be reviewed and advice to maximize adherence will be provided if needed.

The hypocaloric diet will be continued throughout the treatment period. If a  $BMI \leq 22 \text{ kg/m}^2$  is reached, the recommended energy intake should be recalculated with no kcal deficit for the remainder of the trial.

Total energy expenditure is calculated by multiplying the estimated basal metabolic rate (BMR) (see table below) with a Physical Activity Level value of 1.3 (Food and Agriculture Organization of the United Nations/World Health Organization [WHO]/United Nations University 2004), which reflects an inactive lifestyle. This calculation provides a conservative estimate of caloric requirements:

$$\text{TEE (kcal/day)} = \text{BMR} \times 1.3$$

### Equations for Estimating BMR in kcal/Day\*

Sex	Age	BMR (kcal/day)
Men	18 to 30 years	15.057 X actual weight in kg + 692.2
	31 to 60 years	11.472 X actual weight in kg + 873.1
	>60 years	11.711 X actual weight in kg + 587.7
Women	18 to 30 years	14.818 X actual weight in kg + 486.6
	31 to 60 years	8.126 X actual weight in kg + 845.6
	>60 years	9.082 X actual weight in kg + 658.5

Abbreviation: BMR = basal metabolic rate; FAO = Food and Agriculture Organization of the United Nations; UNU = United Nations University; WHO = World Health Organization.

\*Revised WHO equations (adapted from: FAO/WHO/UNU 2004).

### 5.3.2. Physical Activity

At Visit 2 and all subsequent visits, participants will be advised to increase their physical activity to moderate intensity (for example, brisk walking) for at least 150 minutes per week.

### 5.4. Screen Failures

Screen failures are defined as participants who consent to participate in the clinical study but are not subsequently assigned to study intervention. A minimal set of screen failure information is required to ensure transparent reporting of screen failure participants to meet the Consolidated Standards of Reporting Trials (CONSORT) publishing requirements and to respond to queries from regulatory authorities. Minimal information includes demography, screen failure details, eligibility criteria, and any serious adverse event (SAE).

Individuals who do not meet the criteria for participation in this study (screen failure) may not be rescreened.

## 6. Study Intervention

Study intervention is defined as any investigational intervention(s), marketed product(s), placebo, or medical device(s) intended to be administered to/used by a study participant according to the study protocol.

### 6.1. Study Intervention(s) Administered

ARM Name	Tirzepatide MTD	Placebo
Dose	10 mg or 15 mg QW	N/A
Route of Administration	SC	
Sourcing	Provided centrally by the sponsor and dispensed via IWRS	
Packaging and Labeling	Study intervention will be provided in autoinjectors (single-dose pens) packaged in cartons to be dispensed. Clinical study materials will be labeled according to country regulatory requirements.	

Abbreviations: IWRS = interactive web-response system; MTD = maximum tolerated dose; N/A = not applicable; QW = once weekly; SC = subcutaneous.

There are no restrictions on the time of day each weekly dose of study drug is given, but it is advisable to administer the SC injections on the same day and same time each week. The actual date, time, and injection-site location of all dose administrations will be recorded in the diary by the participant. If a dose of study drug is missed, the participant should take it as soon as possible, unless it is within 72 hours of the next dose, in which case that dose should be skipped, and the next dose should be taken at the appropriate time. The day of weekly administration can be changed if necessary, as long as the last dose was administered 72 or more hours before.

All participants will inject study drug SC in the abdomen or thigh using the injection supplies provided; a caregiver may administer the injection in the participant's upper arm. The injection-site location of all dose administrations will be recorded in the diary by the participant. A new autoinjector will be used for each injection. If study drug is to always be injected in the same body region, participants should be advised to rotate injection sites each week.

#### 6.1.1. Medical Devices

The combination products provided for use in the study are tirzepatide investigational autoinjector (or matching placebo). Any AE resulting from device deficiencies, misuse, or malfunctions must be detected, documented, and reported by the investigator throughout the study (see Section 10.4.3).

## 6.2. Preparation/Handling/Storage/Accountability

- The investigator or designee must confirm appropriate storage conditions have been maintained during transit for all study intervention received and any discrepancies are reported and resolved before use of the study intervention.
- Only participants enrolled in the study may receive study intervention. Only study personnel may supply, prepare, or administer study intervention. All study intervention must be stored in a secure, environmentally controlled, and monitored (manual or automated) area in accordance with the labeled storage conditions with access limited to the investigator and authorized study personnel.
- The investigator or authorized study personnel are responsible for study intervention accountability, reconciliation, and record maintenance (for example, receipt, reconciliation, and final disposition records).
- Further guidance and information for the final disposition of unused study interventions are provided in the study training materials.

## 6.3. Measures to Minimize Bias: Randomization and Blinding

This is a double-blind, randomized study.

Participants will undergo a 36-week open-label tirzepatide lead-in treatment period. Those who successfully complete the lead-in period (reaching either a 10-mg or 15-mg dose) will be randomized (1:1) in a double-blind fashion to either continue tirzepatide at MTD or switch to placebo for the duration of the double-blind treatment period. Assignment to treatment groups will be determined by a computer-generated random sequence using the interactive web-response system (IWRS).

The randomization will be stratified by country, sex (female, male), tirzepatide MTD dose at 36 weeks (10 mg versus 15 mg), and percent weight loss at 36 weeks (<10% versus  $\geq 10\%$ ).

Investigators, site staff, clinical monitors, and participants will remain blinded to the treatment assignments of the double-blinded treatment period until the study is complete.

Emergency unblinding for AEs may be performed through the IWRS. This option may be used ONLY if the participant's well-being requires knowledge of the participant's treatment assignment. All emergency unblinding events are recorded and reported by the IWRS.

If an investigator, site personnel performing assessments, or participant is unblinded, the participant must be discontinued from the study. In cases where there are ethical reasons to have the participant remain in the study, the investigator must obtain specific approval from a Lilly clinical research physician (CRP) for the participant to continue in the study.

In case of an emergency, the investigator has the sole responsibility for determining if unblinding of a participant's treatment assignment is warranted for medical management of the event. The participant's safety must always be the first consideration in making such a determination. If a participant's treatment assignment is unblinded, Lilly must be notified immediately. If the investigator decides that unblinding is warranted, it is the responsibility of the investigator to promptly document the decision and rationale and notify Lilly as soon as possible.

## **6.4. Study Intervention Compliance**

Participant compliance with study intervention will be assessed at each visit.

Study drug compliance will be determined by the following:

- Study drug administration data will be recorded by the participant and reviewed by the investigator at each study visit.
- The participants will be instructed to return any unused study drug and/or empty cartons at the next office visit to the study site for the purpose of performing drug accountability.

Treatment compliance for each visit interval is defined as taking at least 75% of the required doses of study drug. Similarly, a participant will be considered significantly noncompliant if he or she is judged by the investigator to have intentionally or repeatedly taken more than the prescribed amount of medication (more than 125%).

In addition to the assessment of a participant's compliance with the study drug administration, other aspects of compliance with the study treatments will be assessed at each visit based on the participant's adherence to the visit schedule, completion of study diaries, and any other parameters the investigator considers necessary.

Participants considered to be poorly compliant with their medication and/or the study procedures will receive additional training and instruction, as required, and will be reminded of the importance of complying with the protocol.

## **6.5. Concomitant Therapy**

Participants will be permitted to use concomitant medications that they require during the study, except certain medications (for example, other medications for weight management, see Section 5.2) that may interfere with the assessment of efficacy and safety characteristics of the study treatments.

Participants who develop diabetes during the study may initiate medication for glucose control, with the exception of dipeptidyl-peptidase-4 (DPP-4) inhibitors or GLP-1R agonists. Initiation of metformin for the treatment of diabetes is permitted, but metformin should not be initiated during the study for the treatment of other metabolic conditions (for example, PCOS, diabetes prevention). Management of incident diabetes should be performed by participants' usual care providers.

Investigative site staff will inform participants that they must consult with the investigator or a designated site staff member upon being prescribed any new medications during the study. This may not be possible when initiated for treatment of medical emergencies, in which case, the participant will inform the investigator or a designated site staff member as soon as possible.

Nonstudy medications taken by participants who are screened but not assigned to study intervention will not be reported to Lilly unless an SAE or AE occurs that the investigator believes may have been caused by a study procedure.

## **6.6. Dose Modification**

### **6.6.1. Tirzepatide**

Tirzepatide is given QW by SC injection. There are no restrictions on the time of day each weekly dose of tirzepatide is given, but it is advisable to administer the SC injections on the same day of the week and similar time each week. If a dose of tirzepatide is missed, the participant should take it as soon as possible unless it is within 72 hours of the next dose, in which case, that dose should be skipped and the next dose should be taken at the appropriate time (see Section 6.1).

Study drug dose modification is not permitted, except for management of intolerable GI symptoms during the 36-week lead-in period (see Section 6.6.2).

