###### ***End of Visit 2 to Visit 11***

At the end of Visit 2, for participants that meet all the entry criteria and are enrolled in this study, study site personnel will demonstrate use of the autoinjector (also referred to as single-dose pen), using the provided demonstration device and observe the study participant inject the first dose of tirzepatide. The date, time, and location of the first dose of study drug will be recorded on the electronic case report form (eCRF).

After study enrollment, participants will undergo a 36-week open-label tirzepatide dose-escalation and lead-in treatment period (Visits 3 to 11 will occur as indicated in the SoA).

Patient-reported outcomes questionnaires should be administered as early as possible, as per Suggested Visit Structure (Section 10.8). Preferred administration order is the same as described for Visit 2. Mental Health questionnaires should be completed after the assessment of AEs.

Dietician consultations continue at Weeks 4, 8, 12, and then as indicated in the SoA (Section 1.3). Study drug and injection supplies will be returned per the SoA and according to local requirements. New supplies will be dispensed as needed.

The starting dose of tirzepatide is 2.5 mg QW for 4 weeks, then the dose is increased by 2.5 mg every 4 weeks (2.5 to 5 to 7.5 to 10 to 12.5 to 15 mg) up to MTD (either 10 mg or 15 mg).

Interventions to optimize study drug tolerance and adherence may be employed throughout the study and include, but are not limited to, brief temporary interruptions and use of additional medications to manage GI symptoms (for example, nausea, vomiting, and diarrhea, see Section 6.6.2 for details). During the open-label lead-in period, participants unable to tolerate 2.5 mg or 5 mg despite the above measures will be discontinued from the study. For participants unable to tolerate any dose between 7.5 mg and 15 mg inclusive, despite the above measures, the investigator should contact Lilly to consider a dose de-escalation step with subsequent re-escalation to reach either the 10-mg or 15-mg dose on or before Week 36 as described below (only 1 cycle of dose de-escalation and re-escalation is permitted during the open-label, lead-in period):

- 7.5 mg to 5 mg, then the dose is increased by 2.5 mg every 4 weeks up to MTD (either 10 mg or 15 mg)
- 10 mg to 7.5 mg, then the dose is increased by 2.5 mg every 4 weeks up to MTD (either 10 mg or 15 mg)

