### **6.6.2. Management of Participants with Gastrointestinal Symptoms**

Participants who experience intolerable GI symptoms (for example, nausea, vomiting, or diarrhea) at any time during the study, should first be counseled on dietary behaviors that may help mitigate nausea and vomiting (for example, eating smaller meals, splitting 3 daily meals into 4 or more smaller ones, and stopping eating when they feel full). If symptoms persist, the participant should be prescribed, at the investigator's discretion, symptomatic medication (for example, antiemetic or antidiarrheal medication). A temporary interruption of study drug for 1 dose is permitted, provided the participant has taken the last 3 weekly doses. Study treatment should be resumed immediately, either alone or in combination with symptomatic medication, which can also be utilized to manage symptoms. Management of study drug after interruptions >1 dose is discussed in Section 7.1.1.

During the 36-week open-label tirzepatide lead-in treatment period, if intolerable GI symptoms (for example, nausea, vomiting, or diarrhea) persist despite the above measures, the investigator should contact Lilly to consider a dose de-escalation step with subsequent re-escalation (Section 4.1.1.2.2). During the 52-week, post-randomization treatment period, dose de-escalation with subsequent re-escalation or dose de-escalation to a lower maintenance dose is not permitted. Those with intolerable GI symptoms that develop after randomization and persist despite the above measures (for example, dietary counseling, symptomatic medication, and interruption of study drug for 1 dose) should discontinue study drug but remain in the study for continued follow-up.

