### 7.1.1. Temporary Discontinuation

In certain situations, the investigator may need to temporarily interrupt study drug. Every effort should be made by the investigator to maintain participants on study drug and to restart study drug after any temporary interruption, as soon as it is safe to do so. Distribution of study medication at the correct dose will be per IWRs instructions.

If study drug interruption is....	and...	then participant...
2 consecutive doses or less	occurs between Weeks 0 and 36	restarts study drug at last administered dose, as per escalation schedule.
2 consecutive doses or less	occurs between Weeks 36 and 88	restarts study drug at chosen MTD at randomization.
3 consecutive doses or more	occurs between Weeks 0 and 36	is not randomized and will be discontinued from study.
3 consecutive doses or more	occurs between Weeks 36 and 88	restarts study drug at 5 mg and repeats dose-escalation scheme to achieve the same MTD assigned at randomization.

Abbreviation: MTD = maximum tolerated dose.

If study drug interruption is due to an AE, then the event is to be documented and followed according to the procedures in Section 10.4 of this protocol.

If study drug interruption is due to intolerable persistent GI AE, participants should be treated as suggested in Section 6.6.2.

Investigators should inform Lilly that study drug has been temporarily interrupted. The data related to temporary interruption of study treatment will be documented in source documents and entered on the eCRF.

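### Protocol 6.6.1 has no exception for the post-randomization restart and re-escalation that 7.1.1 requires, and for GI-related interruptions 6.6.2 and 7.1.1 refer to each other but lead to different outcomes

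*Protocol*

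**What the plan says.** Three places in the protocol govern changes to study drug after randomization.

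- **Section 6.6.1 (Dose Modification, Tirzepatide):** "Study drug dose modification is not permitted, except for management of intolerable GI symptoms during the 36-week lead-in period". The sentence refers the reader only to 6.6.2.
- **Section 6.6.2 (GI symptoms):** for the 52 weeks after randomization, "dose de-escalation with subsequent re-escalation or dose de-escalation to a lower maintenance dose is not permitted". Participants whose intolerable GI symptoms persist despite the listed measures "should discontinue study drug but remain in the study for continued follow-up". The same section also says: "Management of study drug after interruptions >1 dose is discussed in Section 7.1.1".
- **Section 7.1.1 (Temporary Discontinuation):** the table row for 3 or more consecutive doses missed between Weeks 36 and 88 says the participant "restarts study drug at 5 mg and repeats dose-escalation scheme to achieve the same MTD assigned at randomization". The row names no cause. Below the table: "If study drug interruption is due to intolerable persistent GI AE, participants should be treated as suggested in Section 6.6.2". On supply, the section says "Distribution of study medication at the correct dose will be per" the IWRS instructions.

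On the analysis side, the EAS (Protocol 9.3; SAP Section 3) drops data from 7 days after the last dose once study drug has been discontinued. The efficacy estimand (SAP 1.2.1) treats as intercurrent events those that lead to treatment discontinuation.

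**The concern.** A general prohibition with one closed exception sits beside a table row that orders what the prohibition excludes. An investigator who reads 6.6.1 alone would conclude that no dose change is possible after Week 36. One who reads 7.1.1 alone would restart at a lower dose and escalate.

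At stake are the clarity of a dosing instruction and the data that reach the analysis. Whether a participant with a long interruption stops for good or restarts decides whether later weights, possibly including Week 88, count for the efficacy estimand.

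**Working it through.** This is mainly a comparison of texts.

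**Step 1. The plan's own figure.** Protocol 9.2 states more than 90% power for 300 per arm, a 6-point difference, SD 8 and 25% dropout. Evaluable per arm: 300 × (1 − 0.25) = 225. Standard error: 8 × √(2/225) = 0.754. Ratio: 6 / 0.754 = 7.95. Power is above 99.99%, so the stated figure holds. No input to it comes from 6.6.1, 6.6.2 or 7.1.1.

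**Step 2. Is the 7.1.1 restart a dose modification outside the exception?** A randomized participant's MTD is 10 mg or 15 mg. Restarting at 5 mg changes the dose. The exception in 6.6.1 needs two things: intolerable GI symptoms and the lead-in period. The 7.1.1 row applies in Weeks 36 to 88, so the second condition fails whatever the cause.

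**Step 3. The sections side by side, after randomization.**

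| Interruption | 6.6.1 | 6.6.2 | 7.1.1 | Result |
|---|---|---|---|---|
| 2 doses or fewer | No modification | – | Restart at the MTD | No dose change, so no conflict with 6.6.1 |
| 3 or more doses, non-GI cause | No modification | Points to 7.1.1 for gaps over 1 dose | Restart at 5 mg, re-escalate | 7.1.1 readable as the specific rule; 6.6.1 lacks the exception |
| 3 or more doses, GI cause | No modification | Bars step-down with re-escalation; stop drug if symptoms persist; also points to 7.1.1 | Row says restart at 5 mg, re-escalate; text sends persistent GI cases to 6.6.2 | 6.6.1 conflict, and 6.6.2 and 7.1.1 give different outcomes |

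In the last row the two references form a loop, and neither section says which one ends it.

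**Step 4. Effect on the data.**

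- Stop study drug: the participant's EAS data end at last dose + 7 days.
- Restart: later weights remain in the EAS, including those taken before the MTD is regained.

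The treatment regimen estimand uses the full analysis set (FAS) regardless of adherence, so it has no such cut-off.

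**Step 5. Frequency.** Neither document gives or assumes a rate of interruptions of 3 or more doses after randomization, so the number affected cannot be calculated.

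**The case against.** The strongest reply is that the protocol already sorts these cases. The bar in 6.6.2 sits in a section on GI symptoms. Elsewhere the protocol uses de-escalation for a single 2.5-mg step down from a dose that is not tolerated, whereas 7.1.1 concerns resuming after an absence. Section 6.6.2 hands interruptions of more than 1 dose to 7.1.1, and 7.1.1 hands persistent GI cases back. Dose supply follows IWRS instructions, and the sponsor is to be told of every temporary interruption, so sites do not choose the strength.

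Much of this stands, and it rules out some stronger readings that a reader might infer:

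- **That 6.6.2 forbids what 7.1.1 orders for every interruption.** The pointer and the GI setting of 6.6.2 do not support this for non-GI causes.
- **That sites would dispense different doses at will.** IWRS supply limits that, although it does not settle whether a participant with a GI-related gap should stop or restart.
- **That the re-escalation time measures the problem.** With 2.5-mg steps every 4 weeks, regaining the MTD from 5 mg takes (10 − 5)/2.5 × 4 = 8 weeks or (15 − 5)/2.5 × 4 = 16 weeks, which is 15% or 31% of 52 weeks. These figures describe 7.1.1 alone and would be the same if the wording were reconciled in its favour.
- **That the SAP lacks a rule for weights taken below the MTD.** The EAS cut-off depends on discontinuation of study drug, so weights after a restart are already kept.

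The reply does not reach 6.6.1. Dose modification is a wider term than de-escalation, and its one exception does not cover 7.1.1. Nor does it break the GI loop. One could suppose that 6.6.2 governs symptoms that persist and 7.1.1 those that have resolved, but the text does not say so. The GI flowchart in Appendix 9 is not legible in the copy reviewed, so nothing here relies on it.

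**Conclusion.** The point holds as an internal inconsistency in the protocol, in two parts. First, 6.6.1 and the 7.1.1 row for 3 or more missed doses in Weeks 36 to 88 cannot both be followed literally. For non-GI causes this amounts to a missing exception in 6.6.1. Second, for GI-related interruptions after randomization, 6.6.2 and 7.1.1 refer to each other and lead to different outcomes.

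The consequence for analysis is limited to which data enter the EAS, and so to the efficacy estimand. Its size is unknown because no interruption rate is given. Power and sample size are unaffected. The conclusion assumes that restarting at 5 mg counts as a dose modification in the sense of 6.6.1, which is its plain meaning for someone assigned 10 mg or 15 mg.

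**What to change.** The sponsor's clinical team should reconcile 6.6.1, 6.6.2 and 7.1.1 so that one instruction applies to each type of interruption after Week 36, with GI and non-GI causes both addressed and the cross-references no longer circular. Appendix 9 and the IWRS settings should be checked against the result. Which clinical rule applies is for the sponsor to decide.

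The cost is a clarifying protocol amendment, with the ethics approval that Protocol 10.1.1 requires, and notice to sites. The SAP needs no change, because the EAS definition handles either outcome once the protocol is clear.
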